13.2 Sample Size and Statistical Analysis

We have now finished enrolling active patients into the intervention. Our final number of active patients is 27. This is lower than our target enrollment of 45. Therefore, we re-calculated the number of historical controls needed to achieve adequate power for care processes. First we assume the probability of exposure among sampled control subjects is 0.6 and the correlation coefficient for exposure between matched cases and control subjects is 0.3. To detect an odds ratio of 0.26 versus the alternative of equal odds with 27 active patients and a matching sample of 5 historical controls per active patient (totaling 162 active and historical patients combined), and with a Type I error rate of 0.05, the power is 0.80706 (computed using PASS 2024, version 24.0.1).

When analyzing pilot data, descriptive statistics will be run on variables other than our primary and secondary outcomes. When analyzing our primary and secondary outcomes, we will stratify by clinic because they serve communities of differing socioeconomic status. Care processes will be modeled both dichotomously (all relevant completed vs. missing at least one) and continuously (as a percent of indicated care processes that occurred). In analyzing our primary outcome dichotomously, we will use a factorial experimental approach where the guideline-concordant and -discordant measures will be calculated. Additionally, due to the categorical nature of both our primary (dichotomously modeled care processes) and secondary (major and minor amputation) outcomes, we will build a multivariable Poisson regression model. When modeling guideline concordance care processes continuously, we use linear regression. In the primary analysis, we will require patients referred to a vascular or infectious disease specialist to be seen by that specialty, either in-person or via telemedicine, within 2 weeks per our algorithm. We will also conduct an intention-to-treat analysis where we include consults placed but not completed or delayed. Pre/post differences in completed referral rates, coupled with data on why a referral did not take place, will allow us to determine whether referral gaps would be best addressed by focusing on primary or specialty clinic processes.

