7.0 STUDY DESIGN

7.1 General Design

This is a phase II pilot of an integrated care model for treatment of diabetic foot ulcers in rural patient populations and includes adaptive recruitment and retention strategies. The protocol uses a pre-post serial cohort design, where the second and third clinics are activated six months after the first clinic and all clinics complete the trial simultaneously. This design allows: 1) use of refined recruitment and retention strategies when the final two clinics are activated, and 2) dispersion of activation efforts to facilitate completion by small research teams. Subject accrual will occur over 24 months. The design was modified so that clinics 2 and 3 could be activated simultaneously based on 1) our 100% recruitment of healthcare workers from clinic 1, which was greater than expected, and 2) our lower than expected patient recruitment from clinic 1. Having the third clinic activated for longer than initially planned should increase our likelihood of recruiting enough patients into the trial.

The study population will consist of 45 patient participants that develop diabetic foot ulcers during the enrollment period and receive care from participating rural providers (primary care providers (PCPs) at UW Health Belleville and diabetes or wound care providers at Sauk Prairie Healthcare) at rural clinics taking part in the study. Clinic schedulers, in addition to rural providers, will also be enrolled. Patient participants will be eligible only if their rural provider already consented and enrolled in the study. Patient participants will complete screening activities and their rural provider(s) and clinic scheduler will use the integrated care model to assist with care decisions (although rural providers will retain clinic discretion to deviate from the integrated care model to best serve the patient). Study activities include screening, chart reviews, and telephone assessments. Historical control data from up to 180 patients (1:5 active patient enrollment: historical control matching) will be obtained from medical records for comparison. Historical controls will be matched based on clinic and providers but no other factors due to the low overall volume of patients on any one provider's panel with diabetic foot ulcers.

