10.3 Historical Control Patient Participants

10.3.1 Screening and Enrollment

Controls will be matched 1:5 with enrolled patient participants based on clinic and primary care provider and identified through a review of medical records. Additionally, CRDS will be used to screen for historical controls at the UW Health Family Medicine Clinic in Belleville, and data will be delivered to the study team through REDCap. Controls will be identified and selected starting from the date 3 months prior to clinic activation and going back in time until the required number is reached. . The 3-month wash-out will avoid contaminating primary care teams with intervention activation events. Patients receiving palliative care, those unable to provide consent, and those who lacked insurance covering referral to University of Wisconsin specialty clinics will be excluded from the control population consistent with prospectively enrolled patient participants.

A waiver of informed consent and HIPAA authorization waiver has been obtained for data abstraction activities for historical controls. This aspect of the study meets the four criteria for a waiver of HIPAA authorization. First, the research involves no more than minimal risk to the historical controls as it consists of a chart review only. Second, the research could not practicably be carried out without the

waiver since a substantial proportion of the historical controls are likely to have died (~20% in our national cohort study were dead within one year). Third, the research could not practically be carried out without using Identifiable Private Information because we need to access their medical records, which contain the most accurate record of what care they received for their foot ulcer. Fourth, the waiver is unlikely to adversely affect the rights and welfare of the subjects due to the procedures we have in place to maintain the confidentiality of all participants, both historical and prospective.

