13.0 STUDY ANALYSIS

13.1 Statistical Hypotheses

- **Primary Efficacy Endpoint(s):**

- Completion of 5 vascular and 4 infectious disease care processes, modeled as percent indicated and dichotomously (all relevant completed vs. missing ≥ 1). *Hypothesis:* A larger proportion of patients in the integrated care model arm, compared to historical controls, will complete the 5 vascular and 4 infectious disease care processes.

- **Secondary Efficacy Endpoint(s):**

- Amputation, defined as either major or minor. *Hypothesis:* A smaller proportion of patients in the integrated care arm, compared to historical controls, will undergo either major or minor amputation within 3 months of diabetic foot ulcer diagnosis.

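### The stated power of 0.807 belongs to a matched odds-ratio test, but the binary primary endpoint is to be analysed by a Poisson regression with no variance estimator named and no account of the matching

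*Combined protocol and SAP*

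**What the plan says.** All the statistical text is in the combined protocol and SAP.

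- **Power (13.2).** The calculation assumes an exposure probability of 0.6 in controls, and "the correlation coefficient for exposure between matched cases and control subjects is 0.3". For an odds ratio of 0.26, 27 active patients and five controls each, "with a Type I error rate of 0.05, the power is 0.80706". 'Exposure' is not defined. The text does not say whether the odds ratio is marginal or conditional on the matched set, or whether the test is one- or two-sided.
- **Analysis (13.2).** For the binary form of the primary outcome, "we will use a factorial experimental approach where the guideline-concordant and -discordant measures will be calculated". This describes a calculation and names no test. For the categorical outcomes, "we will build a multivariable Poisson regression model". Clinic enters because "we will stratify by clinic because they serve communities of differing socioeconomic status". No covariate list, variance estimator or matched-set term is given here or elsewhere.
- **Matching.** Section 7.1: "Historical controls will be matched based on clinic and providers but no other factors". Section 10.3.1: "Controls will be matched 1:5 with enrolled patient participants based on clinic and primary care provider".
- **Direction (13.1).** "A larger proportion of patients in the integrated care model arm, compared to historical controls, will complete the 5 vascular" and the four infectious disease processes.
- **Synopsis (3.1).** For the same 27 patients and 1:5 ratio it claims power above 0.90 for a rise in completion from 20% to 50%.

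**The concern.** The powered test and the analysed test differ in effect measure (odds ratio against rate ratio) and in their use of the matching. The variance of the second is left open.

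That gap matters because the endpoint is common. Poisson regression takes the variance of a yes/no outcome as p, where the true value is p(1−p). For rare events the difference is negligible. At rates between 0.2 and 0.7 it makes ordinary standard errors clearly too large. With 27 active patients, a real improvement in care could then be missed, and the power for which the control group was enlarged would not be the power of the test that is run. An analyst could equally request robust errors under the same sentence, so the result may depend on a software option that the plan does not fix.

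**Working it through.** **Inputs.** From 13.2: n1 = 27, n0 = 135, odds ratio 0.26, exposure 0.6 in controls, correlation φ = 0.3, alpha 0.05. From the synopsis: 20% vs 50%.

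**Assumption on coding.** Exposure is taken as missing at least one process. Control completion is then p0 = 0.40 and the odds ratio for completion is ψ = 1/0.26 = 3.846. On the opposite reading, an odds ratio of 0.26 would mean worse care, against 13.1. Tests are two-sided.

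**Step 1: completion rate in active patients.**
- Marginal odds ratio: p1 = 0.4ψ/(1 + 0.4(ψ − 1)) = 0.719.
- Set-conditional odds ratio: solve (p1q0 − φs)/(q1p0 − φs) = ψ, with q = 1 − p and s = √(p1q1p0q0). This gives p1 = 0.625. Check: s = 0.2372 and φs = 0.0712, so (0.375 − 0.0712)/(0.150 − 0.0712) is about 3.85.

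**Step 2: reproduce 0.80706.** The power formula for a matched odds-ratio test with M controls per set is Φ{(√n·|e1 − eψ| − 1.96√v1)/√vψ}. Here e and v are the per-set mean and variance of the conditional score under no effect (subscript 1) and under ψ. With n = 27, M = 5 and p1 = 0.625: e1 = 0.4151, eψ = 0.6352, v1 = 0.1745, vψ = 0.1407. The numerator is 1.144 − 0.819 = 0.325; divided by 0.375 this is 0.867, and Φ = 0.807 (0.8071 unrounded). With p1 = 0.719 the result is 0.8029. The stated figure is therefore a two-sided matched odds-ratio power, and the set-conditional reading matches it best.

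**Step 3: size of the Poisson Wald test with ordinary errors.** Model-based variance of the log rate ratio is 1/x1 + 1/x0, where x1 and x0 are the numbers of completers. Full enumeration of two independent binomials (27 and 135) at nominal 0.05 gives size 0.017, 0.009 and 0.002 at common rates 0.2, 0.4 and 0.6.

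**Step 4: power of the same test.** The correct variance for independent patients is (1 − p1)/(n1p1) + (1 − p0)/(n0p0). For 0.72 vs 0.40, the model-based SE is √(1/19.4 + 1/54) = 0.265 and the correct SE is √(0.281/19.4 + 0.6/54) = 0.160. In the table, φ = 0.3 columns are ranges over simulated dependence structures. The set-clustered sandwich uses a 27/26 correction and t with 26 df.

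| Active vs control | SE, model-based | SE, correct | Model-based power, independent | Model-based power, φ = 0.3 | Set-clustered power, φ = 0.3 |
|---|---|---|---|---|---|
| 0.72 vs 0.40 (marginal) | 0.265 | 0.160 | 0.66 | 0.67–0.71 | 0.96–0.99 |
| 0.625 vs 0.40 (set-conditional) | 0.279 | 0.183 | 0.31 | 0.24–0.30 | 0.74–0.87 |
| 0.50 vs 0.20 (synopsis) | 0.333 | 0.258 | 0.81 | 0.85–0.89 | 0.96–0.99 |

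Set-clustered size was 0.033 to 0.046. Conditional logistic regression (Wald) had power 0.94–0.96, 0.67–0.73 and 0.94–0.96 in the three rows. If non-completion is modelled, model-based power with independent patients is 0.54 (marginal) or 0.19 (set-conditional).

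**Step 5: do matching terms in the model help?** With exactly one active patient to five controls in every stratum, clinic, provider or set terms in a Poisson model profile out. In a worked dataset the log rate ratio (0.3857) and model-based SE (0.2937) were the same with none of them and with each of them.

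**Step 6: several sets sharing a provider.** The number of providers is not given; 6, 10 and 15 were assumed, with same-provider correlation 0.3. With stable provider effects, set clustering had size 0.035 to 0.040 at these provider numbers. With a third of the provider variance differing between periods, model-based size ranged from 0.003 to 0.065. Set-clustered size was then 0.10–0.11, 0.07–0.08 and 0.05 with 6, 10 and 15 providers, and provider clustering stayed at 0.03 to 0.06.

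**The case against.** The strongest reply is that the plan never chooses ordinary errors. Robust errors fit the same sentence, so every loss above is conditional. That stands. A reader might infer that the planned analysis is wrong, or that the trial has power of only 0.3; the documents support neither. They support a gap in specification whose consequence is large on one side.

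A reader might also infer that ordinary Poisson errors are always conservative here. They are not: if provider effects move between the historical and active periods, size can reach 0.065 under the assumptions in step 6.

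Nor can it be said that covariates are irrelevant. The invariance in step 5 needs exactly five controls per active patient in each stratum and concerns matching terms only. The model is multivariable with no covariate list, and unbalanced covariates could change the standard error. Stratifying by clinic could also mean separate clinic models, to which these pooled figures do not apply.

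Clustering on provider as the main analysis is tempting but not supported. The number of providers is unknown. With six providers and shifting effects, its power on the marginal reading was 0.40, against 0.62 with ordinary errors, although those do not hold size as reliably. The matching provider is also described inconsistently: 7.1 refers to providers generally, 10.3.1 to the primary care provider, while the participating providers at Sauk Prairie are diabetes and wound care specialists.

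Finally, this is a pilot, and the endpoint is also modelled as a percentage by linear regression, so a missed binary result is not the only chance to see an improvement. That limits the harm, but 13.2 still claims adequate power for care processes.

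**Conclusion.** The concern holds in conditional form. The 0.80706 is the power of a 1:5 matched odds-ratio test and is not established for the Poisson model named for the binary endpoint. With ordinary errors and stable provider effects, that model would generally be too conservative. Power would be about 0.66 on the marginal reading of the odds ratio and about 0.3 on the set-conditional reading, both assuming control completion of 0.40 and that completion is modelled. At the synopsis rates the shortfall is small. A set-clustered robust variance largely removes the loss (0.74 to 0.99 across the same scenarios), so the choice should be fixed before the data are analysed.

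The figures come from two-group comparisons without other covariates, because the plan lists none. False positives are not the main worry unless provider effects shift between periods.

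**What to change.** In 13.2:

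1. Specify log-link Poisson regression adjusted for clinic, with robust (sandwich) variance clustered on matched set, a small-sample correction and a t reference. Conditional logistic regression on the matched sets is an alternative that corresponds to the powered odds ratio.
2. Use the same clustered variance for the linear model of percent completed.
3. Report provider-clustered errors as a sensitivity analysis only, after stating which provider defines the match and reconciling 7.1 with 10.3.1. It guards against the shift in step 6, which set clustering does not fully cover when providers are few.
4. Define 'exposure', say whether the odds ratio of 0.26 is marginal or set-conditional, recompute the power for the chosen model, and restate it in both 13.2 and the synopsis.

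The cost is a few sentences, one software option and a rerun of the power calculation. Matched-set IDs must be kept in the coded dataset, and the stated power may change.

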3.0	06/24/2024	
 1) Updated "[name]" with "[name]" (name and contact info) 2) Updated qualitative retention interview inclusion criteria 3) Updates and additions were made to the qualitative retention interview portion of the interview guide 	
 1) [name] has replaced [name] as research coordinator of the study. 2) We expanded our inclusion criteria and anticipated number of participants for the retention interviews so that we could include key informants from the clinic level, such as administrators. 3) We made some edits/additions after review of the first few retention interviews conducted with patient participants.
3.1	08/28/2024	Increased the number of healthcare worker (HCW) participants and patient participants for qualitative retention interviews by 1 each	A HCW that we'd like to interview was out on medical leave when we were recruiting; she has since returned to work and got back to us expressing interest in participating (and we have the funds to cover additional interviews). We are also increasing our maximum patient participants by one.
4.0	10/14/2024	Changed reimbursement method to Advarra, added patient information letter as a new retention strategy, added qualitative questions to see what patients thought about the new letter	UW policy is mandating switching to Advarra for study reimbursements as of 01/01/2025; initial qualitative interviews of patients suggested we should add a letter to serve as a reminder about the goals of the study and what to expect
5.0	02/06/2025	Updated ratio of active patients to historical controls & removed the date constraint for historical controls; removed [name]'s work phone number	
Per our statistician, with our final number of active patients, we need 135 historical controls for 80% power. We have exhausted our options within the date constraint initially included due to COVID. We think it's more important to be adequately powered and will include COVID as a limitation.
 
[name] will no longer have a dedicated UW number as of 2/28/25

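### The percent-of-indicated primary outcome is analysed by linear regression at 27 versus 135 patients with no variance estimator named; if the group variances differ, the conventional standard error is wrong in either direction

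*Combined protocol and SAP*

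**What the plan says.** Section 13.2 models completion of the care processes in two forms. One is dichotomous; the other is modelled "continuously (as a percent of indicated care processes that occurred"). For the second form the method is a single sentence: "When modeling guideline concordance care processes continuously, we use linear regression". Primary and secondary outcomes are to be stratified by clinic.

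On numbers, the section states "Our final number of active patients is 27" and describes the comparison as "with 27 active patients and a matching sample of 5 historical controls per active patient", which is 5 × 27 = 135 controls. The revision history for version 5.0 gives the same count: "we need 135 historical controls for 80% power".

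The documents name no robust standard error, weighting, unequal-variance method or binomial model for this outcome, and they do not say that model-based standard errors will be used either. They give no SD, variance or mean for the percent score. The stated power covers the dichotomous form only.

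Appendix 10 lists nine processes. Five apply to every patient: pulse examination, smoking status, statin use, baseline plain films and documentation of infection findings. Four apply only when triggered: ABI, vascular surgery visit, treatment of soft-tissue infection, and referral for abscess or osteomyelitis. A patient's denominator can therefore run from 5 to 9.

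**The concern.** A proportion's variance depends on its mean and on its denominator. The conventional linear-model standard error assumes one common variance. With 27 and 135 patients, that variance is estimated with weights 26/160 and 134/160, so about 84% of it comes from the controls. The uncertainty of the difference, however, comes mostly from the smaller active group.

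Two features of the plan make a variance difference likely. The hypothesis in section 13.1 is that completion differs between groups. Section 7.1 matches controls on clinic and provider only, so nothing balances ulcer severity or the number of indicated processes.

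At stake are the confidence interval and p-value for one of the two forms of the primary endpoint. The interval is too wide if active patients are less variable than controls and too narrow if they are more variable. The estimated mean difference itself is unaffected.

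**Working it through.** **1. The plan's own figure.** The stated result is "with a Type I error rate of 0.05, the power is 0.80706". Inputs: 27 active patients, 5 controls each, control probability 0.6 ("we assume the probability of exposure among sampled control subjects is 0.6"), correlation 0.3, odds ratio 0.26. The Dupont matched case-control formula gives 0.803 two-sided and 0.887 one-sided. The two-sided value agrees closely with the stated one. This concerns the dichotomous outcome, so it fixes the sample sizes and candidate rates but says nothing about the variance of the percent score.

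**2. Formula.** Let r be the active variance divided by the control variance, n1 = 27 and n0 = 135. Then

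pooled SE / true SE = sqrt{ [((n1−1)r + (n0−1))/(n1+n0−2)] × (1/n1 + 1/n0) / (r/n1 + 1/n0) }.

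At r = 1 the ratio is 1. With n1 = n0 it is 1 for every r, so the distortion comes from the 1:5 split.

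**3. Different means, same mix of indicated processes.** Here r = p1(1−p1) / [p0(1−p0)]. The rates are the documents' dichotomous or exposure rates read as mean percents, which is an assumption.

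- *60% to 85%* (section 13.2, with the odds ratio inverted to match the hypothesised increase): odds 1.5/0.26 = 5.77, p1 = 0.852, r = 0.126/0.240 = 0.525. Pooled variance factor (26 × 0.525 + 134)/160 = 0.923. Ratio = sqrt(0.923 × 0.04444 / 0.02685) = 1.236, about 24% too large.
- *60% to 28%* (the odds ratio as printed): r = 0.84, ratio 1.06, about 6% too large.
- *20% to 50%* (synopsis): r = 0.25/0.16 = 1.5625. Pooled variance factor (26 × 1.5625 + 134)/160 = 1.091. Ratio = sqrt(1.091 × 0.04444 / 0.06528) = 0.862, about 14% too small.

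**4. No effect, different mix.** With independent processes the variance is proportional to the average of 1/m, where m is the number indicated.

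- *Active 5, controls 7 to 9:* r = 0.2000/0.1263 = 1.58, ratio 0.858, about 14% too small.
- *Active 5–6, controls 6–7:* r = 0.1833/0.1548 = 1.18, ratio 0.945, about 5% too small.

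**5. Simulation.** All runs used 27 versus 135. Those behind the first, second and last rows used 5 to 9 indicated processes; some of the 20% to 50% runs used 4 to 9. Some runs included clinic indicators.

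| Scenario | Conventional SE | Coverage of 95% interval |
|---|---|---|
| 60% to 85% | about 24% too large | about 98.5% |
| 20% to 50% | 12% to 15% too small | about 91% |
| No effect, 5 vs 7–9 | up to about 15% too small | about 91% (type I error about 9%) |
| No effect, 5–6 vs 6–7 | about 5% too small | about 94% |
| Equal means and mix | correct | about 95% |

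Within-patient correlation of 0.1 hardly changes the first two rows. It reduces the two mix-only rows to about 9% and 3% too small. HC3 intervals cover about 94% to 96% throughout. These calculations ignore the matching correlation.

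**The case against.** The strongest case on the other side has four parts.

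- **The plan does not say the standard errors will be ordinary.** A robust variance is compatible with linear regression. This is true: the gap is an unnamed estimator, not a stated wrong one. But conventional standard errors are the usual default, and leaving the choice open allows it to be made after the results are seen.
- **A reader might infer that the variances are unequal by construction.** The documents do not support that. The construction makes variance differ between patients. The groups differ only if mean completion or the mix of indicated processes differs, and with both equal the conventional standard error is right.
- **A reader might put the anti-conservative end at about 20% too small, with type I error near 11%.** That needs active patients with 4–5 indicated processes against controls with 7–9. Appendix 10 has five processes that apply to everyone, so a denominator of 4 is not available. Even 5 against 7–9 is a strong contrast for controls drawn from the same clinics and providers.
- **The consequence is modest.** This is a pilot powered on the dichotomous form, and its non-randomised historical comparison is a larger source of uncertainty. Where the active group nears the ceiling, the error costs precision and creates no false positive.

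The second and third parts stand in full and limit the claim. The first and fourth lower its weight but do not remove it.

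**Conclusion.** The point holds as a conditional one. Section 13.2 leaves the variance estimator unstated for a bounded score with patient-specific denominators at 27 versus 135. Under the trial's own hypothesis that completion differs, the conventional standard error will generally be off.

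Under the plan's own rates the range is roughly 12% to 15% too small to 24% too large. Imbalance in indicated processes alone gives up to about 15% too small, and about 5% in a mild case.

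These are sensitivity values, not properties of the plan. They rest on reading dichotomous rates as mean percents, on assumed mixes of 5 to 9 indicated processes, and on an unmatched analysis. The direction cannot be known before the data are seen. The point is worth correcting because a better-behaved estimator is available at almost no cost.

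**What to change.** Add one sentence to section 13.2: the percent-of-indicated outcome is analysed by the clinic-adjusted linear model, reported as a mean difference, with HC3 heteroscedasticity-consistent standard errors (or an unequal-variance Satterthwaite interval).

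Optionally, name a process-level binomial model with patient-clustered errors as a sensitivity analysis. It weights patients by their number of indicated processes, so it answers a slightly different question and should not replace the mean difference.

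The cost is one sentence and one software option, with no new data. The downside is slightly wider intervals if the variances are in fact equal.
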